Key Exclusion criteria	
Participants meeting any of the following criteria are not eligible for inclusion in this study.
 
 
Any prior or current diagnosis of bipolar disorder, MDD with psychotic features, schizophrenia, or schizoaffective disorder as obtained from M.I.N.I., Module C (Manic and Hypomanic Episodes) and Module K (Psychotic Disorders and Mood Disorders with Psychotic Features) assessed at Screening
 
Patients with acute alcohol or substance use disorder or withdrawal symptoms requiring detoxification, or patients who went through detoxification treatment (inpatient or outpatient) within 1 month before Screening. M.I.N.I. Module I (Alcohol Use Disorder) and Module J (Substance Use Disorder, Non-Alcohol) should be conducted at Screening
 
Participant has a current clinical diagnosis of autism, dementia, or intellectual disability
 
History of seizures. Note: childhood febrile seizures are not exclusionary
 
Participants with current borderline personality disorder as obtained from M.I.N.I., Module Y (Borderline Personality Disorder) assessed at Screening.
 
Participants with suicidal ideation or behavior caused primarily by another non-MDD condition, as obtained from M.I.N.I., Module Z (Suicidality Disorders Classification Interview) assessed at Screening
 
Known worsening or new appearance of suicidal ideation or behavior during a prior treatment with ketamine or esketamine or within 2 months after last ketamine or esketamine administration
 
Active hepatitis B virus (HBV), hepatitis C virus (HCV), human immunodeficiency virus (HIV) or active COVID infection as per medical history and/or available medical records
 
History of hypersensitivity to the study drugs or its excipients or to drugs of similar chemical classes.
 
Participants taking medications prohibited by the protocol (see Section 6.2.2, Table 6-2)
 
Intake of the following medications: 
 
Esketamine or ketamine 2 months before Screening
 
Monoamine oxidase inhibitors (MAOIs) 14 days before Screening
 
 
 
Cardiac or cardiac repolarization abnormality, including any of the following: 
 
History of myocardial infarction (MI), angina pectoris, or coronary artery bypass graft (CABG) within 6 months prior to starting study treatment
 
History of clinically significant cardiac arrhythmias (e.g., ventricular tachycardia), complete left bundle branch block, high-grade AV block (e.g., bifascicular block, Mobitz type II and third degree AV block) within 6 months prior to starting study treatment
 
 
 
Resting QTcF ≥450 msec (male) or ≥460 msec (female) at Screening or pre first dose on Day 1, or inability to determine the QTcF interval
 
Risk factors for Torsades de Pointes (TdP) including uncorrected hypokalemia or hypomagnesemia, history of cardiac failure, or history of clinically significant/symptomatic bradycardia or any of the following: 
 
Long QT syndrome, family history of idiopathic sudden death or congenital long QT syndrome
 
Concomitant medication(s) with a "Known Risk of Torsades de Pointes" that cannot be discontinued or replaced by safe alternative medication 7 days prior to Screening and during the Core.
 
 
 
Participant has mean systolic blood pressure > 140 mmHg or diastolic blood pressure > 90 mmHg at Screening or pre first dose on Day 1; or any past history of hypertensive crisis, or participants in which the elevation of blood pressure or intracranial pressure poses a serious risk e.g. subjects with aneurysmal vascular disease (including intracranial, thoracic, or abdominal aorta, or peripheral arterial vessels); subjects with history of intracerebral haemorrhage
 
Any other condition (e.g. known liver disease/liver dysfunction, active malignancy, etc.) which in the opinion of the investigator would put the safety of the participant at risk, impede compliance or hinder completion of the study.
 

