**Figure 3-1 Study design**

### 3.1 Screening Period

The Screening Period will start when the participant signs the informed consent form. The eligibility of the participant will be determined based on assessments performed at the Screening visit (up to 48 hrs) and also on Day 1 before randomization.

All participants must require hospitalization due to MDD with suicidal ideation with intent. Participants may have already been in the hospital prior to Screening or must agree to hospitalization at Screening.

All participants must receive pharmacological antidepressant SoC, which either has been initiated prior to the study entry or must be initiated or adjusted during the Screening Period, upon signing informed consent.

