  - b. History of clinically significant cardiac arrhythmias (e.g., ventricular tachycardia), complete left bundle branch block, high-grade AV block (e.g., bifascicular block, Mobitz type II and third degree AV block) within 6 months prior to starting study treatment
13. Resting QTcF  $\geq 450$  msec (male) or  $\geq 460$  msec (female) at Screening or pre first dose on Day 1, or inability to determine the QTcF interval

14. Risk factors for Torsades de Pointes (TdP) including uncorrected hypokalemia or hypomagnesemia, history of cardiac failure, or history of clinically significant/symptomatic bradycardia or any of the following:
  - a. Long QT syndrome, family history of idiopathic sudden death or congenital long QT syndrome
  - b. Concomitant medication(s) with a “Known Risk of Torsades de Pointes” that cannot be discontinued or replaced by safe alternative medication 7 days prior to Screening and during the Core.
15. Participant has mean systolic blood pressure > 140 mmHg or diastolic blood pressure > 90 mmHg at Screening and pre first dose on Day 1; or any past history of hypertensive crisis, or participants in which the elevation of blood pressure or intracranial pressure poses a serious risk e.g. subjects with aneurysmal vascular disease (including intracranial, thoracic, or abdominal aorta, or peripheral arterial vessels); subjects with history of intracerebral haemorrhage
16. Any other condition (e.g. known liver disease/liver dysfunction, active malignancy, etc.) which in the opinion of the investigator would put the safety of the participant at risk, impede compliance or hinder completion of the study.
17. Have evidence of significant renal insufficiency, indicated by an estimated glomerular filtration rate (eGFR) of < 40 mL/min/1.73 m^2 at Screening
18. Use of other investigational drugs within 30 days of Screening
19. Pregnant or nursing (lactating) women
20. Sexually active males unwilling to use a condom during intercourse while taking study treatment and for 1 week after stopping study treatment (in the Core and Extension in case of retreatment). A condom is required for all sexually active male participants to prevent them from fathering a child and to prevent delivery of study treatment via seminal fluid to their partner. In addition, male participants must not donate sperm for the period specified above.

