## 8.1 Screening

Screening will be performed while the participant is hospitalized. The duration of the Screening Period is up to 48 hours. In case a safety laboratory assessment at screening is outside of the range specified in the exclusion criteria, the assessment should be repeated prior to randomization on Day 1. If the repeat value remains outside of the ranges specified in the exclusion criteria, the participant must be screen failed.

Investigators may re-screen a participant only once if the investigator is reasonably certain that reasons for screen failure will be resolved prior to or during a repeat screening attempt. Reasons to re-screen may include but are not limited to the following:

- Laboratory value(s) out of range due to sampling error or that might be within range after medically-appropriate supplementation
- The participant has a medical condition that can be stabilized or resolved prior to the repeat screening attempt
- Additional time is required following the participant's last dose of an excluded medication (see [Table 6-2](#))

A participant must provide a new informed consent prior to the initiation of any re-screening procedures (e.g. participant must be reconsented). A new subject number will be assigned.

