  - Post-dose systolic blood pressure of  $\geq 200$  mmHg and/or the DBP is  $\geq 120$  mmHg confirmed by triplicate reading (at least one value should confirm the blood pressure increase above the defined thresholds).

If discontinuation of study treatment occurs, the investigator should make a reasonable effort to understand and record the primary reason for the participant's premature discontinuation of study treatment.

Participants who discontinue study treatment or who decide they do not wish to participate in the study further should NOT be considered withdrawn from the study UNLESS they withdraw their consent (see [Section 9.1.2](#)). Where possible, they should return for the assessments indicated in the Assessment Schedule. If they fail to return for these assessments for unknown reasons, every effort (e.g. telephone, e-mail, letter) should be made to contact the participant/pre-designated contact as specified in the lost to follow-up section.

If the participant cannot or is unwilling to attend any visit(s), the site staff should maintain regular telephone contact with the participant, or with a person pre-designated by the participant. This telephone contact should preferably be done according to the study visit schedule.

Following study treatment discontinuation (no further infusions planned), participants should be followed for two months beyond the 6 week Core Period (Follow-up Period).

Participants who discontinue study treatment during the Core Period should return at every scheduled visit until the End of the 6 week Core Period. The list of assessments should be kept as planned with the following exceptions: ECG and vital signs to be measured (triplicates required), no PK sampling collection, and all assessments that are repeated several times in one day should be done only once [REDACTED]

[REDACTED] Participants will then enter the two months Follow-up Period.

Participants who discontinue study retreatment during the Extension Period should return for the End of Relapse visit and subsequently enter the two month Follow-up Period.

If an onsite visit is not possible, then telephone visits should be conducted and collected at minimum the following:

- New / concomitant treatments
- Adverse Events / Serious Adverse Events

The investigator must also contact the IRT to register the participant's discontinuation from study treatment.

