#### **Post dose blood pressure monitoring:**

The following monitoring criteria based on post-dose blood pressure assessments during the dosing phase should be followed:

[figure not shown]
At 2 hours postdose, if the SBP is  $\geq 160$  mmHg and/or the DBP  $\geq 100$  mmHg, assessments should continue every 30 minutes until:

- The blood pressure is <160 mmHg SBP and <100 mmHg DBP, or
- In the investigator's clinical judgment, the subject is clinically stable or
- The subject is referred for appropriate medical care, if clinically indicated.
- If the blood pressure remains  $\geq 160$  mmHg SBP and/or  $\geq 100$  mmHg DBP, 4 hours after dosing, the subject should be referred for immediate medical treatment.

For patients with SBP  $\geq 180$  mmHg but <200 mmHg and/or the DBP is  $\geq 110$  mmHg but <120 mmHg, further dosing should be interrupted (no subsequent IV infusion given) and the subject should be referred to a cardiologist, or other specialist for a follow-up assessment.

After the assessment by a cardiologist, or other specialist, if recommended by the referring doctor and considered appropriate according to the clinical judgment for the subject to continue in the study, the subject may continue with further dosing only if the predose blood pressure at the next scheduled visit is within the acceptable range.

All follow-up information and procedures performed must be recorded as appropriate in the CRF.

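### Blood pressure exclusion 15 reads *and* in Protocol Section 5.2 but *or* in the Protocol summary, so Section 5.2 taken literally admits a participant above 140/90 mmHg only at the Day 1 pre-dose reading

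*Protocol*

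**What the plan says.** Protocol Section 5.2, criterion 15, sets the limit at mean systolic pressure above 140 mmHg or diastolic above 90 mmHg, "mmHg at Screening and pre first dose on Day 1; or any past history of hypertensive crisis". The Protocol summary lists the same criterion, with the same limits, as "mmHg at Screening or pre first dose on Day 1; or any past history of hypertensive crisis".

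The parts of the Protocol that bear on which wording is meant:

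- Criterion 13 in Section 5.2 (QTcF) covers the same two occasions and uses *or*: "at Screening or pre first dose on Day 1, or inability to determine the QTcF interval".
- Section 3.1 says eligibility is "determined based on assessments performed at the Screening visit (up to 48 hrs) and also on Day 1 before randomization".
- Section 8.1 allows an out-of-range safety laboratory value at Screening to be repeated before randomisation on Day 1: "If the repeat value remains outside of the ranges specified in the exclusion criteria, the participant must be screen failed".
- Table 8-1 schedules blood pressure at Screening and in the Day 1 baseline slot (2 hours before dosing, plus or minus 1 hour). Table 8-3 takes it in triplicate and uses the mean.

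**The concern.** An exclusion that must be met on both occasions is weaker than one that may be met on either. Under the literal Section 5.2 wording, a raised Day 1 pre-dose mean can never exclude a candidate by itself. A hypothetical candidate at 138/88 at Screening and 165/105 pre-dose would pass the numeric part of the criterion, although 160/100 is the level at which Section 10.2.3 calls for extra readings from 2 hours after dosing.

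Section 4.5 reports rises in mean systolic and diastolic pressure at both doses in the proof-of-concept study (0.16 and 0.32 mg/kg), and relies on the eligibility criteria as one of the means of limiting risk. A safety exclusion that reads two ways weakens that reliance. It also leaves sites, and the monitors who verify eligibility, without a single rule: the same candidate could be eligible on one page and a protocol deviation on another.

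**Working it through.** No figure in the plan depends on this wording, so the check is a comparison of the two texts followed by the planned allocation.

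**Step 1: decision table.** *Raised* means that the mean of the triplicate exceeds 140 systolic or 90 diastolic.

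| Screening | Pre-dose Day 1 | Section 5.2 (*and*) | Summary (*or*) | Agree? |
|---|---|---|---|---|
| not raised | not raised | not excluded | not excluded | yes |
| not raised | raised | not excluded | excluded | **no** |
| raised | not raised | not excluded | excluded | **no** |
| raised | raised | excluded | excluded | yes |

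The texts conflict in 2 of 4 combinations, whenever exactly one reading is raised.

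**Step 2: which wording fits the rest of the Protocol.** The summary and criterion 13 both use *or*. Section 3.1 makes Day 1 an eligibility check, which fits *or* better but does not say how two results combine. Amendment 1 states that the summary was updated for consistency with the main body, so the two are meant to match. Its entry for criterion 15 describes only the added serious-risk wording and does not settle the point. The nearest support for *and* is the repeat rule in Section 8.1. That rule is confined to safety laboratory values, and even there the Day 1 value decides. By analogy it could defend admitting someone raised at Screening only (third row). It cannot defend admitting someone raised pre-dose only (second row).

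**Step 3: whether anything else closes the gap before the first infusion.**

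- The serious-risk part of criterion 15 and the whole of criterion 16 are matters of judgement, with no blood pressure figure.
- Section 10.2.3 has one pre-dose gate: dosing may continue "only if the predose blood pressure at the next scheduled visit is within the acceptable range". It applies only to later infusions, after a post-dose reading of at least 180/110, and its range is not given as a number.
- The remaining safeguards begin once dosing has started: readings at 20 and 40 minutes, 4-hour observation, at least 24 hours in hospital, the 160/100 and 180/110 rules in Section 10.2.3, and the 200/120 stopping rule in Section 9.1.1.

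**Step 4: planned exposure of anyone admitted** (arm sizes from Section 12.8.1).

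- Total: 15 + 6 × 30 = 195.
- Active drug at the first infusion: 195 − 30 = 165, and 165/195 = 84.6%.
- 0.16 mg/kg at the first infusion: 30 (every other week) + 30 (single infusion) = 60, and 60/195 = 30.8%.

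Of the four doses in this trial, 0.16 mg/kg is the only one for which the documents report a blood pressure rise. These fractions describe the exposure of any randomised participant. They do not estimate how many pass through the gap.

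**The case against.** The strongest reply is that *and* was meant as an instruction to check on both occasions. Inclusion criterion 6 uses that construction for the MADRS threshold, where it is correct, and carrying it into an exclusion looks like a drafting slip. With *or* in the summary and in criterion 13, many sites may apply *or* anyway, and the eCRF eligibility page, which is not among the documents, may settle it. That is plausible, but it is an argument for correcting the slip: the criterion as written still says something else.

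The clinical stakes can also be put lower. The gating reading is taken about 1 to 3 hours before the infusion, not immediately before it. Section 4.5 puts the peak placebo-adjusted mean change below 20 mmHg, with a clear trend of recovery within 4 hours (diastolic) and 6 hours (systolic). Sections 6.6.2 and 10.2.5 advise against treating transient rises unless clinically indicated. The 20-minute reading falls halfway through the infusion, which can be interrupted for safety, and an investigator may refuse a worrying candidate under criterion 16. All of this stands and limits the likely harm. It does not remove the conflict. Mean changes do not rule out larger individual rises, and these checks are either discretionary or start after dosing has begun.

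It is also fair that only one of the two conflicting combinations, raised pre-dose only, carries the safety argument.

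**Conclusion.** The concern holds. Criterion 15 has two conflicting versions in current text, and the Section 5.2 version, read literally, lets through a participant whose mean blood pressure is above the limit only at the Day 1 pre-dose assessment. Intent is not stated, but *or* is the better-supported reading.

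The number of candidates affected cannot be derived, because the documents give no distribution of Screening or pre-dose blood pressure. Eligibility is decided before randomisation, so the comparison between arms, the power and the alpha are unaffected. This is a wording error in a numeric safety exclusion that should be fixed. It does not threaten the primary analysis. The conclusion rests on reading *and* literally; under the looser sense of checking both occasions, the defect is one of clarity.

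**What to change.** Change *and* to *or* between the two time points in Section 5.2, criterion 15, so that it matches the summary and criterion 13, and send sites a short clarification.

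If the sponsor wants to tolerate a transient raised value at Screening, it should write that as an explicit repeat rule on the model of Section 8.1, use the same text in the summary, and keep a raised pre-dose mean on Day 1 as an exclusion in its own right.

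The cost is one word and a site communication. No procedure is added, because both readings are already scheduled. Sites that have been applying *and* will see some additional screen failures. Their number cannot be estimated from the documents, and the single re-screen in Section 8.1 softens the effect: "Investigators may re-screen a participant only once if the investigator is reasonably certain that reasons for screen failure will be resolved".

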## 6 Treatment

### 6.1 Study treatment

Study treatment consists of MIJ821 or placebo in combination with pharmacological SoC.

MIJ821 20 mg will be centrally supplied as lyophilized powder in vials (pharmaceutical form). This will be reconstituted with 0.9% sodium chloride to obtain the solution for infusion for all MIJ821 doses. Placebo will consist of 0.9% sodium chloride infusion bag supplied by the site.

The first infusion of study treatment (Day 1) must be administered while the participant is hospitalized. All subsequent administrations may be performed either under hospitalization or as an outpatient in the clinic, at investigator's discretion.

